### **7.4 Specimen Collection**

At the baseline visit, Research Coordinators will consent participants if not previously consented, administer the baseline survey, take 3 blood pressure readings, and, obtain a genetic sample via blood draw, saliva or buccal cell collection, whichever is most appropriate for the site and if possible, participant preferences.

#### **Blood Draw Protocol**

A phlebotomist or a coordinator trained in phlebotomy should collect 1 tube (approximately 1-2 teaspoons or 5 mLs) of blood via venipuncture from participants willing to give a blood sample. Research Coordinators should follow the MOP for instructions regarding the collection, storage, and delivery of the genetic samples to the designated laboratory.

#### **Saliva Protocol**

Alternatively, participants may provide a saliva sample in lieu of a blood sample. Research Coordinators should follow the MOP for instructions regarding the collection, storage, and delivery of the sample to the designated laboratory. Patients giving a saliva sample should not eat, drink, smoke or chew gum for 30 minutes before sample collection. Previous studies have confirmed that saliva samples are a viable alternative as a source of DNA for genotyping procedures.

#### **Buccal Cell Protocol**

Alternatively, participants may provide a buccal cell sample in lieu of a blood or saliva sample. Sample collection swabs/brushes should be labeled by recruiters, and collection, storage, and delivery to the designated laboratory

will follow the Buccal Cell Collection Protocol provided in the MOP. Participants providing a buccal cell sample should not eat, drink, smoke, or chew gum for 30 minutes before sample collection.

## **7.5 Specimen Transfer and Genetic Testing Procedures**

All collected specimens should be clearly marked with the participant ID and all other required fields according to the instructions in the MOP, and delivered to a designated laboratory. Samples from Intervention arm participants will be processed by the laboratory as soon as possible using analytically validated *APOL1* and PGx gene testing procedures. For Control arm samples, designated laboratories will either extract DNA as soon as possible after sample receipt, and store the DNA for later analysis or store the sample and extract DNA after the Control participant has completed the 6 month follow-up assessment. Control Arm DNA samples will be processed as soon as possible after the 6 month visit using analytically validated procedures. Genes to be tested for the PGx substudy along with genotyping results and predicted phenotypes are described in Section 7.1. Details of sample storage and transport will be presented in the MOP. All laboratories in GUARDD-US are Clinical Laboratory Improvement Amendments (CLIA)-certified for high complexity.

## **7.6 Return of Genetic Results**

The designated laboratories will transfer participant genetic testing results to the IGNITE PTN Coordinating Center (CC) as soon as possible and follow standard site-specific procedures for return of results to providers. Genetic results will be imported into the study database and the site EHR, where available. The study database will notify study personnel when a participant's lab results are ready to be returned to the participant.

Participants will receive *APOL1* and/or PGx results via phone and/or in-person. Research Coordinators should call participants at the appropriate time (see **Figure 1** and **Tables 5-7**), follow the ROR script (provided in the MOP), and end with a speak back in which participants will explain their results back in order to ensure comprehension. Research Coordinators should note the date, time, and completion status of all RORs in the study database. All participants will receive their genetic test results with lay explanations in writing and an educational booklet explaining their results and genetic risks via mail and/or secure email. Research Coordinators will offer all participants the option to speak by phone or in person with a study genetic counselor about their results. If a participant wants to speak with a genetic counselor, the Research Coordinator should contact the genetic counselor for their site on behalf of the patient, and the genetic counselor should reach out to the patient for counseling.

Providers may be notified of participant results via standard site-specific laboratory return of results methods and, where possible, a CDS within the electronic health system as described in Section 7.8. The genetic testing results should also be stored in the participant's medical records.

## **7.7 Data Collection from the Electronic Health Record**

Data from the local EHR will be used to determine: 1) components of the secondary endpoints (i.e., presence of CKD diagnosis codes in the 24 months prior to baseline and up to 8 months after baseline, urine tests obtained in the 24 months prior to baseline and in the 6 months after baseline), 2) events of interest (see Section 8.2), and 3) variables needed for Other Planned Analyses including Cost Effectiveness Analysis (CEA) (see Section 9.6). Sites will extract the relevant EHR data using prespecified algorithms developed centrally by the IGNITE PTN CC or using site-developed algorithms. If using the CC-developed algorithms, sites will modify the algorithm codes based on their own customized EHR system. Sites will be asked to conduct EHR data downloads after at least 25% of the participants have completed their 6 month visit, and approximately 6-12 months after the last patient is randomized. EHR results will be sent to the IGNITE PTN CC via secure data transfer and formatted for data analyses. Details of the EHR download and transfer process will be provided separately to relevant site personnel.

## **7.8 Clinical Decision Support System**

While participants will be notified of their *APOL1* and PGx test results via a phone call and/or in-person, providers may be notified of participant results via standard site-specific laboratory return of results methods and, where possible, a CDS within the electronic health system. For *APOL1* testing, sites should work with their institutional informational technology departments to set up provider CDS alerts for positive *APOL1* results and for actionable PGx phenotypes when a relevant medication is ordered. *APOL1* alerts should include the participant's *APOL1* status, the risks associated with the participant's *APOL1* status, and treatment recommendations (including treatment for elevated BPs, ordering urine proteins tests, and ordering ACEs/ARBs), and additional educational materials delivered via the site-specific CDS implementation method. For PGx testing, provider alerts should indicate the participant's genetic results, the predicted phenotype (i.e., efficacy of various hypertension medications), and treatment recommendations.

Reflecting the pragmatic nature of the trial, the many involved research sites, and variations in local CDS policies, it is anticipated that there will be differences in CDS implementation details, but all sites will ensure that both participants and providers are alerted to *APOL1* and PGx test results and associated significance. Details of the alerts will be provided separately to relevant site personnel.

## **7.9 Provider Surveys**

Providers that agree to participate in the baseline survey should be given a written baseline survey to complete or instructions for completing the baseline survey online.

## **7.10 Schedule of Activities**

Providers should be recruited and asked to complete the baseline survey as soon as possible after site activation. CDS alerts for providers should be activated as soon as lab results are entered into the electronic health record.

**Tables 5, 6, and 7** describe the participant schedule of events for GUARDD-US.

**Table 5.** Schedule of participant activities up to randomization for sites.

Activities	Prior to baseline	Baseline visit
Recruit participants	X	X
Screen potential participants for interest/eligibility	X	X
Contact participant to schedule baseline visit	X	X
Obtain consent	X	OR X
Obtain BP & pulse & return BP results to participant		X
Distribute educational booklet/s to participant		X
Administer baseline participant survey		X
Perform sample collection		X
Randomize to APOL1 treatment at end of baseline visit & notify patients of their randomization assignment		X

**Table 6.** Schedule of activities following participant baseline visit for sites participating in the PGx substudy.

Activities	CONTROL GROUP				INTERVENTION GROUP											
					APOL1 Positive				APOL1 Negative PGx Control Group				APOL1 Negative PGx Intervention Group			
	After Baseline & before 3M visit	3M visit (+8 wks)	6M visit (+8 wks)	After 6M visit	After Baseline & before 3M visit	3M visit (+8 wks)	6M visit (+8 wks)	After 6M visit	After Baseline & before 3M visit	3M visit (+8 wks)	6M visit (+8 wks)	After 6M visit	After Baseline & before 3M visit	3M visit (+8 wks)	6M visit (+8 wks)	After 6M visit
Participant surveys, BP & pulse measurements, & return of BP results to participant		X	X			X	X			X	X			X	X	
APOL1 testing conducted at laboratory				X	X				X				X			
Return APOL1 test results to participant verbally and with written explanation				X	X				X				X			
Give educational booklet for APOL1 results via mail or secure email				X	X				X				X			
PGx testing conducted at laboratory				X	X				X				X			
Return PGx Results verbally and with written explanation				X				X				X	X			
Give educational booklet for PGx results via mail or secure email				X				X				X	X			

**Table 7.** Schedule of activities following participant baseline visit for sites participating not in the PGx substudy.

Activities	CONTROL GROUP				INTERVENTION GROUP			
	After Baseline & before 3M visit	3M visit (+8 wks)	6M visit (+8 wks)	After 6M visit	After Baseline & before 3M visit	3M visit (+8 wks)	6M visit (+8 wks)	After 6M visit
Participant surveys, BP and pulse measurements, & return of BP results to participant		X	X			X	X	
APOL1 testing conducted at laboratory				X	X			
Return APOL1 test results to participant verbally and with written explanation				X	X			
Give educational booklet for APOL1 results via mail or secure email				X	X			

## **8. SAFETY ASSESSMENT AND MONITORING**

GUARDD-US is an observational-type study that does not include a drug or device intervention. For this reason, no adverse events will be collected or recorded in the study database. Distress from return of results and events of interest will be monitored (as described in the next sections) and a Data and Safety Monitoring Board (DSMB) will provide trial oversight. Adverse events suspected to be related to study interventions should be reported to the reviewing IRB following local policies. Reportable events including unanticipated study related deaths will be collected in the study database per IRB reporting policies.

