## **2.2 Aims and Objectives of the Study**

Because AAs are not routinely screened for *APOL1*, it is unknown whether participant or provider knowledge of genetic risk impacts participant care or outcomes. Accordingly, the main objective of GUARDD-US is to determine the effect of participant and provider knowledge of a positive *APOL1* status on BP, urine testing for CKD, and documented diagnosis of CKD.

The primary aim is to determine the effect of participant and provider knowledge of a positive *APOL1* status and accompanying guideline based clinical decision support (CDS) on blood pressure management on change in systolic blood pressure (SBP) from baseline to 3 months after randomization among the *APOL1* positive participants. Secondary aims are to:

1. Determine the effect of participant and provider knowledge of a positive *APOL1* status on the probability of documented CKD diagnosis.
2. Determine the effect of participant and provider knowledge of a positive *APOL1* status on the probability of receiving a urine microalbumin/creatinine testing and ACE-I/ARB prescription based on results of the urine microalbumin level.
3. Explore cost effectiveness, mediators, moderators, psychobehavioral impact of results disclosure on participants, and effects of participant and provider knowledge of *APOL1* status on provider treatment recommendations.

In addition, GUARDD-US will include a substudy to determine the effect of knowledge of genetic test results that predict efficacy of various antihypertensive medications on change in SBP from baseline to 3 months in *APOL1* negative individuals.

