#### Participants

- An educational booklet given to all participants at the baseline visit that includes information about high blood pressure, kidney disease, and *APOL1* gene testing, and language recommending that participants speak with their provider if their BP is >130/80 mm Hg.
- The results of participant blood pressure readings at each study visit including
  - the mean of the second and third blood pressure readings
  - an indication of whether the mean value is normal (<130/80 mm Hg), up to your provider (between 131/81 mm Hg and 140/90 mm Hg) or elevated (>140/90 mm Hg)
  - a recommendation to speak with a provider if the participant's BP is above normal
- The verbal return of *APOL1* genetic testing results (i.e., *APOL1* positive or negative) and a verbal explanation of the meaning of the genetic testing results for risk of CKD and hypertension to participants following the schedule of activities and procedures for the participant's *APOL1* randomization assignment (see Section 7.10).
- A written explanation of the clinical implications of the patient's *APOL1* genetic testing results given to participants at the time of ROR.
- The same educational booklet will be given to participants as a reminder at the time of ROR.
- The option for patients to speak with a genetic counselor about their results.

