#### Providers

- The return of PGx genetic testing results to patient providers via standard site-specific laboratory return of results methods at approximately the same time or after participants have received their PGx testing results.

- Where possible, a CDS provider alert for actionable phenotypes when a relevant medication is or may be ordered that indicates the participant's genetic results, the predicted phenotype (i.e., efficacy of various hypertension medications), and treatment recommendations at approximately the same time or after participants have received their PGx testing results.

**Tables 2 and 3** describe the genes, variants, and phenotypes for the PGx substudy. The PGx sub-study will examine the efficacy of providing genetic information for two gene-drug pairs. The first gene-drug pair is *YEATS4* and thiazide diuretic efficacy, and focuses on first-line antihypertensive therapy in African Americans. The second gene-drug pair is *NAT2* and hydralazine. Hydralazine is not first line therapy, but is used in the treatment of resistant hypertension. GUARDD-US will include patients with both hypertension and resistant hypertension. Neither gene-drug pair is presently recommended by CPIC, but both have significant evidence supporting their relationship in populations that include individuals of African ancestry which is summarized in **Appendix B**.

**Table 4** describes the PGx recommendations to be given for actionable genotypes. Each recommendation will be provided in the laboratory return of results and via a CDS alert, where available, that will be activated when a provider prescribes a medication that is not recommended based on the participant's genotype. Please see section 7.6 for more details.

**Table 2.** Genes and gene variants to be tested in the PGx substudy.

Gene	Variant
NAT2	rs1801279, rs1801280, rs1799930, rs1799931
YEATS4	rs7297610

**Table 3.** PGx genotypes, phenotypes, and predicted genotype frequencies.

Gene	Genotyping Result	Predicted Phenotype	Phenotype Frequency
NAT2	1 or more copy of *4	Reduced Hydralazine Efficacy	0.50
NAT2	2 copies of *5, *6, *7, *14 b	Increased Hydralazine Efficacy	0.50
YEATS4	T/T or T/C	Reduced Thiazide Efficacy	0.51
YEATS4	C/C	Standard Thiazide Efficacy	0.49

**Table 4.** PGx recommendationsa

Goal (Drug Class)	Gene	Genotype	Recommendation

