First Line Therapy (Thiazide diuretic)	YEATS4	C/C	This individual is predicted to have standard thiazide efficacy. Consider use of a thiazide diuretic or calcium channel blocker as first line treatment of hypertension.
First Line Therapy (Thiazide diuretic)	YEATS4	TT or TC	This individual is predicted to have reduced thiazide efficacy. Consider use of an alternate first line therapy such as a calcium channel blocker for treatment of hypertension.
Resistant Hypertension (Hydralazine)	NAT2	*4/*X	This individual is predicted to have reduced hydralazine efficacy and may require a 50-100% higher starting dose or an alternate agent such as clonidine, spironolactone, or doxazosin for resistant hypertension.
Resistant Hypertension (Hydralazine)	NAT2	2 non-*4 alleles	This individual's NAT2 genetic test result is associated with increased hydralazine levels, which may lead to increased efficacy and/or adverse effects.

aDetailed references and rationale are summarized in Appendix B

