## 7.2 Baseline Assessments

At baseline, which may occur in a location agreed upon between potential participants and the research team, Research Coordinators will verify that the participant has given consent. If participant has not given consent, Research Coordinators will obtain consent and information for multiple methods of patient contact (including mailing address, all phone numbers, and next of kin contact information). Research Coordinators will administer a survey (approximately 30 minutes long) to obtain information regarding the demographics, comorbidities, psychosocial factors, and knowledge, attitudes and beliefs towards genomics, kidney disease and hypertension. Survey responses will be recorded by the Research Coordinator in the study database and may be administered over the phone. A paper version of the survey can be used during a study visit, with survey data entered into the study database at a later time. Blood pressure will be measured according to the GUARDD-US Blood Pressure Protocol (details provided in the MOP) using a digital blood pressure monitor (such as Professional Intellisense Blood Pressure Monitor, OMRON-907). Manual blood pressures may be collected if necessary. Pulse measurement will also be recorded for each participant and a blood, saliva, or buccal cell sample will be collected (as described in Section 7.4). After completion of the baseline visit, the Research Coordinator will randomize participants to immediate or delayed *APOL1* genetic testing and give patients: 1) an educational booklet with information about high blood pressure, kidney disease, and *APOL1* gene testing, 2) the results of participant blood pressure readings including the mean of the second and third blood pressure readings and an indication of whether this measurement is normal (<130/80 mm Hg), up to provider (between 131/81 mm Hg and 140/90 mm Hg) or elevated (>140/90 mm Hg), and 3) the participant's randomization assignment.

During the baseline visit, if the third (3rd) of three (3) consecutively measured blood pressure readings is greater than or equal to 190 mmHg for SBP or greater than or equal to 110 mmHg for DBP, study staff must inform the participant that they have very high blood pressure and strongly advise that they get urgent and appropriate evaluation and care from a healthcare provider. Study staff must also inform study PIs and follow the elevated blood pressure protocol outlined in the MOP.

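### Participant BP feedback has no lower bound: a hypotensive visit reading is returned as normal, without advice, in a trial whose results and alerts prompt antihypertensive treatment

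*Combined protocol and SAP*

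**What the plan says.** **BP feedback.** Under Section 7.1, each participant receives the mean of the second and third readings at every visit, with "an indication of whether the mean value is normal (<130/80 mm Hg), up to your provider" as the first two of three bands. The third, elevated, is above 140/90. Section 7.1 then adds "a recommendation to speak with a provider if the participant's BP is above normal". Section 7.2 repeats the bands for the baseline visit. No band has a floor.

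**Urgent rule.** Section 7.2 requires staff to act when the third reading "is greater than or equal to 190 mmHg for SBP or greater than or equal to 110 mmHg for DBP". Section 7.3 repeats this for follow-up visits, and Section 6.7 gives the same two limits. Details are left to the MOP.

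**Prompts to treat.** Section 7.8 says *APOL1* alerts should carry "treatment recommendations (including treatment for elevated BPs, ordering urine proteins tests, and ordering ACEs/ARBs". Section 2.2 includes in a secondary aim "and ACE-I/ARB prescription based on results of the urine microalbumin level". PGx recommendations come with an alert that, where available, "will be activated when a provider prescribes a medication that is not recommended based on the participant's genotype". For carriers of the *NAT2* \*4 allele, Table 4 says the person "may require a 50-100% higher starting dose or an alternate agent such as clonidine, spironolactone, or doxazosin for resistant hypertension".

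**Safety collection.** Section 8 states that the study "does not include a drug or device intervention. For this reason, no adverse events will be collected or recorded in the study database". It also keeps IRB reporting of suspected related events, database capture of reportable events, distress monitoring, EHR review of emergency department (ED) visits and hospitalizations, and DSMB oversight.

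**The concern.** The trial supplies no drug, but it is built to change drug treatment. Its own pilot, described in Section 2.1, found that participants reported taking more BP medicines after positive than after negative results. The foreseeable harm of more antihypertensive treatment is a pressure that is too low, yet every rule for an individual reading looks upward. The feedback does more than stay silent about a low reading: it tells the participant that the reading is normal. A participant with light-headedness and a low study reading would be reassured by study staff when a call to the provider was needed. What is at stake is patient safety at the visit. The validity of the primary comparison is not in question.

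**Working it through.** **1. Apply each rule to an example mean of 85/55 mm Hg** (third reading taken to be the same).

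| Rule | Trigger | Result at 85/55 |
|---|---|---|
| Feedback band (7.1, 7.2) | below 130/80 is normal | labelled normal |
| Advice to speak with a provider (7.1) | BP above normal | no advice |
| Booklet advice (7.1) | BP above 130/80 | no advice |
| Urgent rule (7.2, 7.3) | SBP ≥190 or DBP ≥110 | no action |
| Risk section (6.7) | SBP above 190 or DBP above 110 | no action |

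The interim boundary in Section 9.7 does not fill the gap. It compares groups, and a larger SBP fall in the Intervention arm counts towards efficacy.

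**2. Who is exposed.** The feedback is the same in both arms and goes to all randomised participants. Control participants receive no results before the 6-month visit, but Section 7.1 notes that anyone may be treated for hypertension in routine care.

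**3. Reproduce the plan's analysis size, used below as a denominator.** Inputs from Sections 9.1 and 9.7: difference 3.5 mm Hg, SD 18.1, power 80%, final alpha 0.0492, 10% loss.

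- n per arm = 2 × (1.9668 + 0.8416)² × 18.1² / 3.5² = 421.9, so 422.
- Total 2 × 422 = 844. With loss, 844 / 0.90 = 937.8, so 938. Both match the plan.
- PGx arms: 946 × 0.90 = 851 per arm.

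**4. Possible number of low readings at 3 months.** The documents give no rate, so a range of 1% to 5% is assumed.

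- *APOL1* positives: 422 × 0.01 = 4.2 and 422 × 0.05 = 21.1 per arm.
- PGx arms: 851 × 0.01 = 8.5 and 851 × 0.05 = 42.6 per arm.

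**5. Precision of an optional by-arm table.** The 95% half-width for a risk difference is 1.96 × √(2p(1−p)/n).

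| Outcome (assumed risk) | *APOL1* positives | PGx arms |
|---|---|---|
| Low SBP, 1% to 5% | n = 422: 1.3 to 2.9 points | n = 851: 0.9 to 2.1 points |
| ED visit or hospitalization, 5% to 20% | n = 469: 2.8 to 5.1 points | n = 946: 2.0 to 3.6 points |

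Low study-visit SBP is the more direct measure. All-cause acute care is less precise and not specific to low BP.

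**The case against.** The strongest objection is that the MOP, which holds the BP protocol and the elevated-BP protocol, is not in the file and may contain an instruction for low readings. That stands as a limit. It does not remove the point, because the protocol itself fixes the feedback bands, and those call any low value normal.

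It is also fair that 85/55 is hypothetical, that the documents give no frequency, and that eligibility requires a provider who manages the participant's hypertension (5.2). The *APOL1* alerts concern elevated BP. The higher hydralazine dose aims at equivalent control (Appendix B), so over-treatment is not intended. These facts bound the size of the problem. They do not make the label right.

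A reader might infer several stronger things that the documents do not support:

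- *Safety is not monitored.* Section 8 keeps the safeguards listed above. Its statement that the study includes no drug intervention is literally true, and rewording it would change no procedure.
- *No by-arm safety analysis will be done.* Section 9 states none, but Section 8.3 assigns safety monitoring to a Data and Safety Monitoring Plan and a DSMB SAP, and Section 9.2 assigns detail to a separate SAP. A table may exist there.
- *Safety counts will mix time before and after Control disclosure.* The synopsis allows EHR retrieval for up to 12 months, and Control results follow the 6-month visit. However, no section proposes counting events over the whole period. The by-arm cost analysis in 9.6, limited to *APOL1* positives, uses 6 months.
- *The labelling biases the primary result.* It is identical in both arms.

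**Conclusion.** The point holds as a defect in participant feedback. On the protocol's text, a hypotensive study-visit reading is returned as normal, with no advice and no escalation, in either arm, while the returned results and alerts recommend BP treatment, ACE/ARB orders and, for some PGx results, a higher hydralazine starting dose. If 1% to 5% of 3-month readings were low, about 4 to 21 *APOL1*-positive participants per arm and about 9 to 43 per PGx arm would be affected at that visit. The labelling defect follows from the stated thresholds and does not depend on that range. Its practical weight depends on two unknowns: what the MOP says, and how many participants are still in follow-up under version 6.0.

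**What to change.** For participants still in follow-up:

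1. In Sections 7.1 and 7.2, give the normal band a lower bound, for example SBP 90 mm Hg, with the final value set by the clinical team. Add a low category with advice to contact the provider, promptly if there are symptoms.
2. Mirror this in the MOP rule, so that staff have an instruction for low readings as well as high ones. If the MOP already has one, align the feedback bands with it.

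**Cost.** A change to the feedback form and MOP, IRB approval, a notice to about 46 to 60 sites, and some contacts for symptom-free low readings. The change applies alike to both arms and leaves the primary estimate, alpha and power as they are.

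**Optional.** If neither the DSMB SAP nor the study SAP has it, add one by-arm table in *APOL1* positives and one in the PGx arms: low study-visit SBP, any ED visit and any hospitalization. Count ED and hospital events over a fixed interval from randomisation, for example 6 months. Stopping at each participant's 6-month visit would give unequal exposure, since that visit may be up to 8 weeks late. Report risk differences with 95% confidence intervals and no p-values, consistent with Section 9.9. BP, ED and hospitalization data are already planned, so this adds analysis work only.
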